#### D. STATISTICS ANALYSIS

Categorical data is analyzed by Chi-square test, and continuous data is analyzed by T test. If the baseline characteristics are similar, the chi-square test can be used directly to compare the incidence rates between the group of exposure and the group of non-exposure, to conclude if there is a correlation between the exposure factor and outcome. In a meanwhile, calculate the relative risk and 95% confidence interval in order to further illustrate the degree of correlation. In contrast, if the baseline characteristics of exposure group and non-exposure group are different, multiple factor linear regression should be used to control the

mixing factors. If there is no time variation in the data, logistic linear regression can be used to adjust the baseline characteristics of the groups which are different in the model. If there are time variations in the data, Cox linear regression should be used to adjust the baseline characteristics of the groups which are different in the model.

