### **B. STUDY DESIGN AND METHOD**

**—STUDY DESIGN:** A Prospective Multicenter Observational Cohort Study —**METHODS**:

**Period:**3 years, including 6 months for building up Network platform and database, 30 months for the follow-up with an interval of at least once every 6 months done for every patient and updating the database timely.

[figure not shown]

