#### Clinical pathologic data:

- 1). Characteristics of epidemiology (Age, reproductive history, menstrual history, body parameters)
- 2). Diagnostic criteria (pathology, transvaginal ultrasonography or magnetic resonance image)
- 3) Semeiology and evaluative criteria (vision algetic standard (VAS); pictorial blood loss assessment chart (PBAC))
- 4) Surgical approach and perioperative reproductive techniques program
- 5) Medical treatment
- 6) Reproductive choices and fertility outcomes
- 7) Symptom improvement, quality and satisfaction of Life
- 8) Malignant transformation
- 9) Menopausal symptoms and Hormone therapy
- 10) Systematic assessment of the side effects

Picture 1. Network platform (NP) and database Building

- 2. Based on the database imformations, 30-month follow-up will be done for every patient, trying to analyze the problems below: 1) The diagnostic strategies for AM;2) Selection of therapeutic scheme;3) Etiology of AM and endometriosis;4)The study of histology, molecular and genetics about AM and endometrial receptivity.
- 3. The Follow-up visits is standardized, and the contents include :1) The therapeutic efficacy, complication and side-effect of different treatments;2)The fertility outcomes of different reproductive choices;3) AM &menopausal symptoms and hormone therapy; 4) Relevant issues among malignant transformation of AM.
- 4. According to the data above, intensive training courses about AM will be organized regularly, finally propeling the formation of Expert Consensus and Clinical Guidelines about AM which suitable to chinese conditions.

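### Section D makes confounder adjustment depend on baseline looking similar, with no criterion, so comparisons in an observational cohort may be reported unadjusted

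*Combined protocol and SAP*

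**What the plan says.** Section B describes the design as "A Prospective Multicenter Observational Cohort Study". No section mentions randomisation. Section C, item 3, lists what follow-up will examine, including "The therapeutic efficacy, complication and side-effect of different treatments" and fertility outcomes by reproductive choice. Item 4 says the data are to feed an expert consensus and clinical guidelines.

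Section D is the whole analysis plan. It opens with a general rule: "Categorical data is analyzed by Chi-square test, and continuous data is analyzed by T test". It then sets out two branches.

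- **Baseline similar.** "If the baseline characteristics are similar, the chi-square test can be used directly to compare the incidence rates between the group of exposure". The comparator is the non-exposed group. Alongside this the analyst is to "calculate the relative risk and 95% confidence interval in order to further illustrate the degree of correlation".
- **Baseline different.** "if the baseline characteristics of exposure group and non-exposure group are different, multiple factor linear regression should be used to control the" confounders, which the text calls mixing factors. For data without a time element, "logistic linear regression can be used to adjust the baseline characteristics of the groups which are different in the model". For data with one, "Cox linear regression should be used to adjust the baseline characteristics of the groups which are different in the model".

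No section says how similarity is judged (test, cut-off or standardised difference), which characteristics are checked, or which confounders are always adjusted for.

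**The concern.** Treatment in this cohort is chosen, not allocated, so confounding is the main threat to every comparison. Section D recognises this but lets the observed baseline table decide what is done about it.

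- **The trigger.** If baseline is judged similar, the unadjusted result may stand as the result. Failing to see a difference in a small comparison is weak evidence of balance, and several small imbalances in the same direction can add up.
- **The selection.** On the most natural reading, the logistic and Cox models include only the characteristics that differ. A variable that strongly predicts outcome but narrowly escapes being flagged is left out.

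At stake is whether a reported treatment difference reflects treatment or case mix, in results meant to support guidance. A lesser issue is that Section D names a relative risk beside the chi-square test but no effect measure for the regressions, so different comparisons may be reported on different scales.

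**Working it through.** **Inputs.** From the documents: an observational design (Section B), the comparisons (Section C, item 3), the rule (Section D), and 5000 women with at least 200 per centre (Section A). The plan gives no significance level, event rate, exposure split or size for any comparison, so there is no plan figure to reproduce. Everything below rests on assumed values.

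**Step 1: how easily imbalance passes as similar.** Take a standardised mean difference (SMD) of 0.1, 250 per group and a two-sided baseline test at 0.05.
- Noncentrality = 0.1 × √(250/2) = 1.118.
- Chance of being flagged = Φ(1.118 − 1.960) + Φ(−1.118 − 1.960) = 0.200 + 0.001 = 0.201.
- Chance that all six of six independent confounders escape = 0.799^6 = 0.26. The simulation below also gives 26%.

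**Step 2: what an unadjusted comparison then carries.** With no true effect and one binary confounder of prevalence p0 (unexposed) and p1 (exposed) that multiplies risk by R, crude RR = [1 + p1(R − 1)] / [1 + p0(R − 1)]. For p0 = 0.30, p1 = 0.40 and R = 3 this is 1.8/1.6 = 1.125. With 100 per group, a baseline test at 0.05 calls that confounder similar 68% of the time.

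**Step 3: the whole rule, by simulation.** Independent normal confounders, logistic outcome model, pooled risk 40%, no exposure effect, 250 per group, SMD 0.1 per confounder unless stated, flagging by t test at p<0.05. If nothing is flagged, a chi-square test is used. Otherwise logistic regression is used with the flagged variables only (narrow reading) or with all confounders (broad reading). Fixed adjustment always uses all confounders. Ranges span repeat runs with different seeds.

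| Assumed confounders (OR per SD) | Narrow | Broad | Fixed | Crude |
|---|---|---|---|---|
| Six of OR 2, same direction | 12.6–13.1% | 7.6–7.7% | 4.9–5.3% | 33.7% |
| Six of OR 1.5 | 8.6–9.0% | 6.6% | 5.0–5.3% | 19.5% |
| Six of OR 1.3 | 6.1–6.9% | 5.4–5.6% | 4.8–5.3% | 12.5% |
| Two of SMD 0.4 plus four of 0.1, OR 2 | 7.7–8.5% | 4.9–5.0% | 5.0–5.4% | 85.5% |
| Two of OR 2 | 5.9% | not run | 5.0–5.5% | 10.0% |
| Six of OR 2, three against three | 3.8–3.9% | not run | 4.8–5.2% | – |

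The largest narrow and fixed runs used 10,000 replicates (Monte Carlo SE 0.2–0.3 points). The broad runs used 2500–4000, for which √(0.076 × 0.924/2500) = 0.5 points. In the first row, the 26% of datasets that pass as similar have a mean null RR of about 1.13.

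By group size, the first row on the narrow reading against fixed adjustment gives 8.5% v 5.7% at 100 per group, 14.6% v 4.8% at 500, 10.9% v 4.8% at 1000 and 5.9% v 5.2% at 2500.

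**Step 4: dependence on the unstated cut-off.** In the first-row setting on the narrow reading, flagging at p<0.01, 0.05, 0.10 or 0.20 gives 23.9%, 12.7%, 8.8% or 5.7%, against 5.3% fixed. The share passing as similar is 25.1% at 0.05 and 11.7% at 0.10. The cut-offs are nested, so 25.1 − 11.7 = 13.4% of datasets take different branches.

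**Step 5: effect scale.** OR = [p1/(1 − p1)] / [p0/(1 − p0)] with p1 = 1.5 × p0, where p0 and p1 are now outcome risks. At p0 = 1%, 20% and 40%, a true RR of 1.5 is an OR of 1.51, 1.71 and 2.25. The scale matters only for common outcomes.

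**The case against.** The strongest reply is that the plan does foresee confounding and that the text is less restrictive than it looks.

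- **The word only is not in Section D.** In the logistic and Cox sentences, the clause about being different can attach to the groups: once the groups differ, adjust for baseline characteristics. The preceding sentence on controlling mixing factors supports this. A reader might infer that the models certainly adjust for nothing but the differing characteristics. The documents do not settle that. On the broad reading the case with two large imbalances shows no inflation. What survives either way is the similar branch, which has no adjustment.
- **The wording is permissive.** The chi-square test may be used directly, and adjustment is not forbidden. This stands, so the claim is that results may be reported unadjusted, not that they will be.
- **The main illustration is unfavourable.** Six independent confounders all acting one way is a hard case, and the fixed comparator adjusts for every true confounder, which no real list guarantees. In a separate simulation with four binary confounders (30% v 38%, log OR 0.8 each), narrow against fixed was 6.5% v 5.3% at 100 per group and 6.4% v 6.1% at 400. With large imbalances the similar branch is almost never reached.
- **Different branches are not different conclusions.** A reader might infer from the 13% that two analysts would often disagree. In a repeat run with 14% branch splits, a split came with a different significance verdict in only 1.7% of datasets (0.4% at OR 1.3). Verdicts differed in 5.3% overall (1.4% at OR 1.3), mostly through covariate choice on the narrow reading.
- **The scale point is inference.** Section D never mentions an odds ratio, and its relative-risk sentence is not expressly confined to the similar branch. It is therefore secondary.

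The total of 5000 does not answer the concern, because the plan does not give the size of any single comparison.

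**Conclusion.** The point holds and should be fixed. Section D gives a rule under which an observational comparison may be reported without adjustment because baseline looked similar, and it sets no criterion for that judgement. This part is certain from the text. Adjustment limited to the differing characteristics is the more natural reading of the logistic and Cox sentences, but not the only one.

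On the assumed inputs, type I error in the unfavourable case is about 13% (narrow) or 7.7% (broad) against 5% with fixed adjustment. For six confounders of OR 1.3 it is about 6.5% or 5.4%. It is near nominal with two confounders of OR 2 and not inflated when directions are mixed. The documents cannot say where the real comparisons fall.

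Two stronger readings are not supported. The plan does not ignore confounding: its rule removes much of it, as the gap between the narrow and crude columns shows. Nor is the choice between logistic and Cox models at fault, since it follows whether the data vary over time and not baseline balance.

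**What to change.** Delete the similarity condition from Section D. For each exposure-outcome comparison:

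- List the confounders before analysis, on subject-matter grounds, from data that Section C already collects: age, reproductive and menstrual history, body parameters, and VAS and PBAC where recorded before treatment.
- Exclude variables that may be consequences of treatment, and use a smaller set for rare outcomes such as malignant transformation.
- Make the adjusted estimate with its 95% confidence interval the main result whatever the baseline comparison shows: an adjusted relative risk for binary outcomes, a hazard ratio for time-to-event outcomes and a mean difference for continuous outcomes.
- Keep the crude chi-square test and relative risk as descriptive.

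The cost is SAP wording, a short confounder list per comparison and a little more analysis, with no extra patients or visits. Some confidence intervals will widen. At 250 per group and an assumed 40% risk there are 500 × 0.40 = 200 events, so exposure plus six confounders leaves 200/7 = 28.6 events per term. Rare outcomes will support only a few confounders. Section C does not say when VAS and PBAC are recorded, so they can be used only where a pre-treatment value exists.

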# A. OBJECT

5000 women diagnosed of Adenomyosis(AM) with pathology or magnetic resonance image (MRI) will be enrolled from nationwide multicenter. Each center should recruite at least 200 patients.

— **PATHOLOGY**: Adenomyosis can be present diffusely throughout the myometrium, or confined to a discrete area. Upon sectioning the uterus, the myometrial wall appears thickened and often contains small hemorrhagic or chocolate colored areas representing islands of endometrial bleeding. The term cystic is used to describe either diffuse adenomyosis or adenomyomas for which with cysts >5 mm in diameter.

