## C. TECHNICAL ROUTE

1. **Build up database basing on the Network platform.** Licensed research centers recruite patients according to the consistent universal diagnostic criteria, and then extract and register clinical pathologic data from their medical records system after getting their informed consent. Limited sharing platform for the database entry would be built by expert network firms, making it available for sub-centers to access the database and download relevant data. Ultimately, on the premise of research results sharing, we could carry out clinical scientific research development and summary nationwide. [Picture 1.]

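### When baselines are judged similar, incidence is compared by crude chi-square and relative risk with no allowance for unequal follow-up; the plan considers time only when baselines differ

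*Combined protocol and SAP*

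**What the plan says.** Section D first asks whether the exposure groups are alike at baseline. If so: "If the baseline characteristics are similar, the chi-square test can be used directly to compare the incidence rates", accompanied by a relative risk and 95% confidence interval. Regression enters only on the other side of that question: "In contrast, if the baseline characteristics of exposure group and non-exposure group are different". Within that side a second criterion applies. "If there is no time variation in the data, logistic linear regression can be used"; where there is time variation, "Cox linear regression should be used to adjust the baseline characteristics of the groups which are different". Both regression models are described as ways to adjust for baseline differences. No time-to-event or person-time method is named for groups that are alike.

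On timing, section B gives a period of "3 years, including 6 months for building up Network platform and database, 30 months for the follow-up". Section C, item 2 says "30-month follow-up will be done for every patient". Section C, item 1 places recruitment within the database-building step ("Licensed research centers recruite patients according to the consistent universal diagnostic criteria"). Section A sets the target: "5000 women diagnosed of Adenomyosis(AM) with pathology or magnetic resonance image (MRI) will be enrolled". The available text gives no opening or closing date for enrolment and no rule for dropout, censoring or missing outcomes. A figure in section B is not shown.

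**The concern.** Baseline balance bears on confounding. Whether every woman was observed for the same length of time is a separate question, and balance does not answer it. By naming Cox regression for data with time variation, the plan accepts that follow-up time can matter, but as written it acts on this only where baselines differ.

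Two routes to unequal follow-up are open. A woman enrolled after month 6 cannot complete 30 months inside the 3-year period. And women may be lost during 30 months of visits. In either case a simple proportion with events does not in general estimate the 30-month risk.

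The outcomes affected include fertility outcomes, complications, side effects and malignant transformation, compared across treatments that were not randomised. Section C, item 4 intends the results to feed a consensus and guidelines, so the absolute risks matter as well as the ratios.

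**Working it through.** The plan states no event rate, loss rate, group size or power, so there is no figure of its own to reproduce. The timeline comes from the documents; every other input below is assumed for illustration.

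**Timeline.** 6 + 30 = 36 months = 3 years. A woman enrolled k months after month 6 has 30 − k months available. For all 5000 to have 30 months, enrolment must finish by month 6: 5000 / 6 ≈ 833 per month if spread over the set-up period. This is not claimed to be infeasible.

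**Differential loss, no true effect.** Assumed: everyone enrolled by month 6; the same constant monthly hazard h in both groups; independent exponential loss reaching 10% in group 1 and 20% in group 2 by month 30.

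- True 30-month risk = 1 − exp(−30h).
- Loss hazard c = −ln(1 − loss)/30, giving 0.00351 and 0.00744 per month.
- Observed event proportion p = h/(h + c) × [1 − exp(−30(h + c))].
- Completers without an event: q = exp(−30(h + c)).

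Denominator A counts everyone enrolled, with lost patients as non-events: risk = p. Denominator B counts events plus completers: risk = p/(p + q).

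| h per month | True risk | A: 10% v 20% loss | A: RR | B: 10% v 20% loss | B: RR |
|---|---|---|---|---|---|
| 0.001 | 3.0% | 2.81% v 2.65% | 1.059 | 3.11% v 3.30% | 0.943 |
| 0.003 | 8.6% | 8.18% v 7.73% | 1.058 | 9.04% v 9.56% | 0.946 |
| 0.01 | 25.9% | 24.66% v 23.36% | 1.056 | 27.00% v 28.27% | 0.955 |
| 0.03 | 59.3% | 56.76% v 54.07% | 1.050 | 60.80% v 62.44% | 0.974 |

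Worked line, h = 0.01, 10% loss: p = 0.2466; q = exp(−0.3) × 0.9 = 0.6667; B = 0.2466/0.9133 = 0.2700.

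Under A the crude risk is 95-96% of the true risk with 10% loss and 90-91% with 20% loss. Under B it is too high in both groups.

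**False-positive rate under A** (two-sided 5% pooled two-proportion test, hazards in the order of the table):

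- 500 per group: 5.3, 5.8, 7.7, 13.7%.
- 2,500 per group (all 5000 split equally): 6.3, 9.0, 19.1, 48.3%.
- Equal loss in both groups: RR 1.00 and 5%.

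**Late entry, same in both groups, no loss.** Assumed: true 30-month risk 20%, entry uniform over 12 months, common closing date, denominator A. With λ = −ln(0.8)/30 = 0.00744, crude risk = 1 − 0.8 × [exp(12λ) − 1]/(12λ) = 16.3%. The RR under no effect stays at 1; the absolute risk is understated.

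**Censoring-aware alternative.** In simulated data with the differential-loss settings (4,000 studies in each of 8 settings), the log-rank test rejected in 4.9-5.5% of studies, and the ratio of mean Kaplan-Meier 30-month risks was 0.99-1.00.

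**The case against.** The plan promises every patient 30 months and places recruitment in the database-building step. If that is achieved without loss, all share one horizon and a chi-square test with RR at that horizon is a standard choice. The figure that is not shown may also bear on the schedule. All of this stands, so unequal follow-up is a possibility and not a finding.

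The wording is permissive, and in an observational comparison of treatments the groups will often differ at baseline, where the plan already calls for Cox regression. This narrows the reach of the problem. It does not remove it, because no other method is named for groups that are alike.

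A reader might infer that baseline similarity alone selects the method throughout. It does not: it selects crude analysis or regression, and time variation then selects logistic or Cox regression where baselines differ.

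A reader might also infer that the plan's crude incidence must be too low. That requires lost patients to be counted as non-events, and section D states no denominator. With events plus completers the direction reverses. With only those still in contact at month 30, and loss independent of outcome, there is no bias.

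Finally, the 48.3% false-positive rate should not be read as a forecast. It needs all 5000 women in one equally split comparison, a 59% event risk and denominator A, none of which the documents give.

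**Conclusion.** The gap is real and should be fixed. Section D offers no censoring-aware method where baselines are similar, although unequal follow-up is possible on the stated timeline and loss is not addressed.

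Its size is conditional. With late entry or loss, absolute risks can be distorted in a direction set by the unstated denominator. Under the assumed 10% v 20% loss, the ratio under no effect moves to 1.05-1.06 or to 0.94-0.97. It moves only if follow-up or loss differs by exposure group, which the documents do not show. For uncommon outcomes the consequence is small at moderate group sizes: counting lost patients as non-events, the false-positive rate is 5.3-5.8% at 500 per group for true risks of 3.0-8.6%. If all women are enrolled by month 6 and none are lost, there is no harm.

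Confidence is medium, because the loss rates, hazards and group sizes are assumed.

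**What to change.** Apply section D's time criterion whether or not baselines are similar:

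- Where follow-up is incomplete or unequal, analyse incidence outcomes by Kaplan-Meier or cumulative incidence with log-rank or Cox, censoring at last contact. Give risk and RR at a pre-stated horizon.
- Keep chi-square or logistic regression for outcomes with complete follow-up to a fixed horizon, and state the denominator.
- Confirm that enrolment, event and last-contact dates are captured. Section C lists data domains, so they may already be.
- Allow for event dates known only to the interval between visits, which are planned at least every 6 months.
- Report loss by exposure group.
- Either fix enrolment to close by month 6, or restate follow-up as running to a common closing date, up to 30 months.

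The cost is protocol and SAP wording, a check of the data fields, and slightly more analysis work, with no added patients or visits. If follow-up is restated, it reads slightly less favourably. The methods still assume that loss is unrelated to the outcome given the covariates, which is why loss by group needs reporting.

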# E. QUALITY CONTROL MEASUREMENT AND RESULT PUBLICATION

- 1. Every center of the research possesses the competence of scientific research to conduct clinical studies. Special people from each center will be put in charge of the research and monitoring the whole procedure. The rights and interests, responsibility and obligation of all centers will be standardized with the research agreement.
- 2. The maintenance, secrecy and safety of Network platform and database will be guaranteed by Department of Obsterics and Gynecology, Peking Union Medical College Hospital.
- 3. Every center is responsible for the database building, and required to finish the prospective follow up for 200 patients at least.
- 4. The researchers' findings will be released in a paper published online.

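### Section D leaves centre out of both analysis branches of a non-randomised multicentre cohort, so treatment comparisons can be too precise, and biased, to the extent that adjusted covariates do not explain centre differences in outcome

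*Combined protocol and SAP*

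**What the plan says.** Section D is the whole analysis plan, and it has two branches.

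- **Crude branch.** The condition is "If the baseline characteristics are similar". Then "the chi-square test can be used directly to compare the incidence rates between the group of exposure and the group of non-exposure", with a relative risk and its 95% confidence interval. Continuous data get a t test.
- **Regression branch.** If the groups differ at baseline, a linear model is named for confounding. Without a time element, "logistic linear regression can be used to adjust the baseline characteristics of the groups which are different in the model". With one, "Cox linear regression should be used to adjust the baseline characteristics of the groups which are different in the model".

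Neither branch names centre as a covariate, stratum, cluster or random effect. Elsewhere, centres appear only in connection with recruitment, data entry, follow-up duties and quality control.

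Section B calls the design "A Prospective Multicenter Observational Cohort Study". Section A sets 5000 women as the total and adds: "Each center should recruite at least 200 patients". Section E, item 3, says each centre is "required to finish the prospective follow up for 200 patients at least". Section C lists choice of treatment among the questions to be analysed, and the efficacy and side effects of different treatments among the follow-up contents.

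**The concern.** Treatment is not randomised, so how often each treatment is used may differ from centre to centre. Outcome risk may differ by centre too, through referral pattern, case mix or skill. If both vary, a pooled comparison of treated with untreated women is partly a comparison of some centres with others. One omission then has two consequences.

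- **Precision.** The pooled interval treats 5000 women as independent and ignores the centre component of the contrast.
- **Bias.** If centres that favour a treatment also have higher or lower risk for other reasons, the estimate shifts.

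Treatment comparisons are where this matters most. Section C, item 4, says the data are meant to lead to a consensus and clinical guidelines.

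**Working it through.** **Inputs from the documents.** Total enrolment is 5000 and the minimum per centre is 200 (Sections A and E). Follow-up is described as "30-month follow-up will be done for every patient" (Section C). The confidence level is 95% (Section D). If enrolment is 5000 and every centre reaches 200, there are at most 5000/200 = 25 centres. The plan gives no power, effect size or event rate, so it has no figure of its own to reproduce.

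**Assumed inputs.** 25 centres of 200, 50% exposed, 40% with the outcome, no true effect. The exposure ICC (rx) and outcome ICC (ry) are varied.

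**Step 1: crude branch, centre effects independent.** Variance inflation is 1 + (200 − 1) × rx × ry. Coverage is 2Φ(1.96/√inflation) − 1.

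| rx / ry | Inflation | Coverage, formula | Coverage, simulated pooled RR |
|---|---|---|---|
| 0 / 0.05 | 1.00 | 95.0% | 94.7% |
| 0.01 / 0.01 | 1.02 | 94.8% | 94.8% |
| 0.05 / 0.01 | 1.10 | 93.8% | 93.9–94.2% |
| 0.1 / 0.02 | 1.40 | 90.3% | 90.4–90.5% |
| 0.1 / 0.05 | 2.00 | 83.5% | 83.5% |

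Where a range is shown, it spans two separate simulations. The t test behaves alike: 93.7% at 0.05/0.01 and 83.9% at 0.1/0.05. The Mantel-Haenszel RR stratified by centre stays at about 95%. A further simulation with 40% exposed and about 20% risk gave 81.7% for the crude RR at 0.1/0.05. It stayed near 95% when only exposure or only outcome varied by centre.

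**Step 2: crude branch, centre effects correlated (ICCs 0.1/0.02).** For correlation c, the risk difference shifts by c × √(0.1 × 0.25) × √(0.02 × 0.24) / 0.25 = 0.0438c.

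- c = 0.3: 1.3 percentage points, RR ≈ 0.4066/0.3934 = 1.03.
- c = 0.5: 2.2 percentage points, RR ≈ 0.411/0.389 = 1.06.

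The standard error of the pooled log RR is √(2 × 0.6/(0.4 × 2500)) = 0.0346, so the interval reaches only about 7% either side (1.96 × 0.0346 = 0.068). With the true standard error √1.40 times larger, these shifts give coverage of about 80% and 62%. Simulation gives RR 1.03 and 1.05, with coverage of about 81% and 65%. The shifts are small in absolute terms; coverage falls because the interval is narrow at 5000 women.

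**Step 3: regression branch.** The logistic model is adjusted for one covariate that differs between groups. Simulated coverage without centre depends on how much of the between-centre outcome variation that covariate explains.

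| ICCs | None | Half | All |
|---|---|---|---|
| 0.05 / 0.01 | 93.8% | 93.8% | – |
| 0.1 / 0.02 | 89.9% | 91.7% | 95.2% |
| 0.1 / 0.05 | 82.3% | 89.7% | 95.1% |

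With centre as a fixed effect, coverage is 94.3–95.9%. A Cox model with 30-month censoring and none explained gives 93.5% down to 85.2% over a similar ICC range; stratified by centre it gives 94.0–95.3%.

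**The case against.** The strongest defence is that Section D names no covariate at all, so the absence of centre is weak evidence that it would be omitted. Read broadly, the baseline characteristics could include centre. An exposure that follows centre would then fail the similarity condition and go to regression. A reader might therefore infer from my point that the plan excludes centre; the text does not support that. What stands is that nothing says centre is included, and a literal analyst would leave it out.

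A reader might also infer that intervals are too narrow wherever exposure and outcome both vary by centre. That is false for the regression branch: when the adjusted covariates explain all the between-centre outcome variation, coverage is about 95%.

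The crude branch may seldom apply to treatment. If similarity were judged by a significance test (an assumption), 2500 against 2500 would flag differences above about 1.96 × √(2/2500) = 0.055 SD, and most treatment comparisons would go to regression. That moves the problem without removing it, as Step 3 shows.

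Common diagnostic criteria, standardised visits and the centre agreement (Sections C and E) should reduce differences in ascertainment between centres. They do not standardise treatment choice or case mix.

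Finally, every ICC is assumed and the loss is near zero at low values. That limits the size of the point, but not the gap in the plan.

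**Conclusion.** The concern holds in a conditional form. Followed literally, Section D leaves centre out of both branches. Treatment comparisons then have intervals that are too narrow to the extent that exposure and outcome both vary by centre and the adjusted covariates leave centre differences in outcome unexplained. If treatment preference and risk are related across centres, estimates are biased as well.

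The plausible size runs from negligible (ICCs 0.01/0.01) to a nominal 95% interval covering about 83.5% (0.1/0.05), and lower with correlated centre effects. There is no material harm for exposures unrelated to centre. None of the ICCs, prevalences or correlations comes from the documents. The figure of 25 centres is also conditional: it needs enrolment of 5000 and at least 200 women in every centre. This is worth correcting before analysis, but it does not show that any particular result will be wrong.

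**What to change.** State in Section D that treatment (exposure) comparisons account for centre, as follows.

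- **Crude categorical comparisons:** Cochran-Mantel-Haenszel test and Mantel-Haenszel RR stratified by centre, in place of the pooled chi-square and RR.
- **Crude continuous comparisons:** a linear model with centre as a factor, in place of the t test.
- **Linear and logistic models:** centre as a factor, with conditional logistic regression for sparse outcomes.
- **Cox models:** stratified by centre.
- **Exposures set wholly by centre:** centre-clustered standard errors with a small-sample correction, and a statement that centre confounding cannot be removed.

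**Cost.** The change needs SAP wording and a centre identifier in the analysis dataset, which centre-based data entry (Section C) implies but does not state. Intervals are about 0–9% wider at exposure ICCs up to 0.1, and about 18% wider for the crude RR at 0.3. Centres that use only one treatment do not contribute to the contrast.
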